## **6.2.2 Serious Adverse Events**

All serious events must be reported as described in Section 6.2.2.2 and recorded in the appropriate electronic Case Report Form (CRF) in the EDC system InForm, and electronically signed by the investigator within 24 hours of event awareness. In case of EDC system unavailability the sponsor’s SAE Form must be used. An SAE requires expeditious handling to comply with regulatory requirements. Any SAEs occurring from the signing of the ICF through 30 days after the last dose of study drug will be captured and must be reported to the Shire Pharmacovigilance Department and the Shire Medical Monitor within 24 hours after the investigator is made aware of the event.

### **6.2.2.1 Serious Adverse Event Definition**

An SAE is an AE that results in any of the following outcomes:

- Death
- Is life-threatening. A life-threatening AE is any AE that places the subject—in the investigator’s opinion—at immediate risk of death from the reaction as it occurred. It does not include a reaction that, had it occurred in a more serious form, might have caused death.
- Persistent or significant incapacity or substantial disruption of ability to conduct normal life functions
- Hospitalization or prolongation of existing hospitalization
- Congenital anomaly/birth defect

- Important medical events that may not result in death, be life threatening, or require hospitalization may be considered an SAE when, based upon appropriate medical judgment, they may jeopardize the subject or may require medical or surgical intervention to prevent one of the other outcomes listed in this definition. Examples of such medical events include allergic bronchospasm requiring intensive treatment in an emergency room or at home, blood dyscrasias or convulsions that do not result in hospitalization, or the development of drug dependency or drug abuse.

Scheduled and/or elective hospitalizations occurring under the following circumstances will not be defined as SAEs for this clinical study:

- planned before entry into the clinical study
- are for elective treatment of a condition unrelated to the studied indication or its treatment
- occur on an emergency, outpatient basis and do not result in admission (unless fulfilling the previous criteria)
- are part of the normal treatment or monitoring of the studied indication and not associated with any deterioration in condition

#### **6.2.2.2 Procedures for Reporting Serious Adverse Events**

Within 24 hours of becoming aware of ANY SAE (regardless of its relationship to investigational product) that occurs during the course of the clinical study from the time the subject signs the ICF through 30 days after the study drug is completed, the investigator must notify the sponsor. The SAE information will include the description of the event and the date that the investigator became aware of the event. Supplemental data (eg, medical records or lab values, if applicable) will be faxed/emailed to Shire Pharmacovigilance and Risk Management Department, if requested by the sponsor. This ensures timely reporting of applicable reports to Health Authorities.

Note: Minimum criteria for reporting an SAE are the SAE term, an identifiable subject, a suspect investigational medical product (study drug), and a reporter. Hospitalization is not an AE, but a serious event criterion. The SAE term is the medical event that led to the hospitalization. Surgery is not an adverse event, but the event that required the subject to have surgery is the SAE term. Death is not an SAE, but an outcome.

The investigator is responsible for notifying the local, regional, or country-specific authorities of all SAEs and device failures that occur at his or her site, as required by local regulations.

All SAEs must be reported, whether or not they are considered causally related to the study drug. Appropriate clinical, diagnostic, and laboratory measures should be performed to delineate the cause of the SAE in question and the results reported. Follow-up for the SAE should occur at appropriate intervals until the event/laboratory abnormality:

- Returns to baseline or
- Becomes stable to a clinically acceptable level that is safe for the subject.

The investigator is required to assess the causal relationship of each reported SAE, to the study drug (see Section 6.2.1.3). A causality assessment should always be included on the sponsor's

SAE form. The investigator should make the causality assessment based on the information available at the time of the event. The causality can be updated at a future date if additional information is received.

The causality categories are:

Not related

- May or may not follow a reasonable temporal sequence from administration of the study product
- Is biologically implausible and does not follow a known response pattern to the suspect study product (if response pattern is previously known)
- Can be explained by the known characteristics of the subject's clinical state or other modes of therapy administered to the subject

Related (Possibly Related/Probably Related/Related)

- A single occurrence of an event that is uncommon and known to be strongly associated with drug exposure (eg, angioedema, hepatic injury, Stevens-Johnson Syndrome)
- Follows a reasonable temporal sequence from administration of the study product
- May follow a known response pattern to the study product (if response pattern is previously known)
- Could not be reasonably explained by the known characteristics of the subject's clinical state or other modes of therapy administered to the subject, if applicable
- Recurs upon rechallenge after withholding and then reintroducing study product

Contact information for SAE reporting and emergency contact details can be found at the beginning of the protocol and in the Study Reference Manual.

As required by International Conference of Harmonisation (ICH) guidelines and global health authorities, the sponsor or designee will notify investigators of all adverse drug reactions that are serious, unexpected, and deemed by the reporting investigator or sponsor to be related to study drug (suspected, unexpected, serious, adverse reaction [SUSAR]). Causality, while assessed, does not negate reporting requirements to the sponsor. An AE, whether serious or not serious, is designated unexpected (unlabeled) if it is not reported in the clinical safety section of the Investigator Brochure (IB) or if the event is of greater frequency, specificity, or severity than is mentioned in the IB. The investigator will receive a copy of the current valid version of the IB prior to the start of the study; however, the investigator will not be required to assess expectedness, nor should expectedness impact the investigator reporting SAEs within the timeframe herein defined.

Upon receiving such notices, the investigator must review and retain the notice. As per the Food and Drug Administration (FDA) *Guidance for Clinical Investigators, Sponsors, and IRBs, Adverse Event Reporting to IRBs-Improving Human Subject Protection, January 2009* if it is

determined that there is an unanticipated signal, the Shire SMT will analyze the data and prepare a summary supporting the determination and interpretation of the findings. The sponsor or designee will send this summary to the investigators with instructions to provide it to their IRB.

The investigator should also comply with the IRB procedures for reporting any other safety information (ie, autopsy reports).

Shire will be responsible for submitting SUSAR reports to the appropriate health authorities. These reports will be submitted within the expedited timeframe. All fatal and life-threatening SUSAR reports will be submitted by Shire or designee within 7 days of receipt (Day 0) of the initial report. All other SUSAR reports will be submitted by Day 15 following the event.

### 6.2.3 Laboratory Evaluations

The following laboratory tests will be performed. Final RELAY study parameters may be used as baseline parameters for this study. Subjects from the REPLACE study who did not participate in the RELAY study will have to complete Visit 1 procedures. All laboratory tests collected during the study will be analyzed by a central laboratory, with the exception of all urine pregnancy tests and total serum calcium levels obtained at baseline and interim time points for safety checks, which will be done at the investigators' or subjects' local laboratories. The following laboratory parameters will be collected according to the schedule of procedures as noted below and outlined in [Table 6-1](#) and [Table 6-2](#):

- Hematology (fasted): hemoglobin concentration, hematocrit, erythrocyte count, platelet count, and leukocyte counts with differential (baseline, Week 52, every 12 months during the long-term extension, and at the End of Treatment visit).
- Serum Chem-20 panel (fasted): alanine transaminase, aspartate transaminase, alkaline phosphatase, lactate dehydrogenase, inorganic phosphate, total and direct bilirubin, creatine kinase, blood urea nitrogen, glucose, electrolytes (sodium, potassium, chloride, and bicarbonate), creatinine, calcium (standard and albumin-corrected), magnesium, total protein, albumin, and uric acid (baseline, Week 52, every 12 months during the long-term extension, and at the End of Treatment visit).
- Urinalysis: specific gravity, pH, protein, glucose, ketones, bilirubin, urobilinogen, blood, and microscopic analysis of sediment (baseline, Week 52, and at the End of Treatment visit).
- Creatinine clearance (baseline, Weeks 16, 32, and 52, every 4 months during the long-term extension, and at the End of Treatment visit).
- Total serum calcium (local) (baseline, interim Week 1, as needed at any other time during the study, and at the poststudy interim visit)
- Total serum calcium, albumin, and phosphate (every visit through Week 52; calcium and phosphate only at every long-term extension visit and at the 1-week follow-up visit)
- Serum potassium, sodium, and calcium (1 week and again 1 month following the institution or change in dose of the calcium-sparing diuretic and then at each subsequent scheduled clinic visit)
- Serum 25 (OH) vitamin D levels (every visit through the End of Treatment visit)

- Serum 1,25-dihydroxyvitamin D levels (Weeks 24 and 52, every 6 months during the long-term extension, and at the End of Treatment visit).
- 24-hour urine calcium, phosphate, sodium, and creatinine (baseline, Weeks 16, 32, and 52, every 4 months during the long-term extension, and at the End of Treatment visit).
- Serum bone turnover markers (BSAP, s-CTx, P1NP, and osteocalcin) (baseline, Weeks 8, 16, 24, 40, and 52, every 4 months during the long-term extension, and at the End of Treatment visit).
- Serum beta human chorionic gonadotropin ( $\beta$ -HCG) pregnancy test (women of child-bearing potential [WOCBP] only) (baseline, Weeks 16, 24, 32, 40, 48, 52 and End of Treatment visit)
- An FSH test to confirm postmenopausal status, if necessary (baseline only)
- Urine pregnancy test (WOCBP only) (baseline, Weeks 4 and 8, and every 2 months during the long-term extension)
- PTH and ECP antibodies (predose at baseline, Weeks 24, 40, 52, every 6 months during the long-term extension, and at the End of Treatment visit)
- Serum PTH[1-84] for PK analysis (Week 48 only)

Clinically significant (as determined by the investigator) abnormal laboratory test results will be considered AEs. A result outside of the normal range may be repeated for confirmation. Any laboratory test result that meets the criteria for an SAE (see Section 6.2.2.1) must also be recorded in an SAE report so that the sponsor or designee can collect additional information about that abnormality, including information regarding relationship to investigational product or other causes, any action taken, and outcome.

#### **6.2.4 Vital Signs and Body Weight**

Vital signs will be measured prior to blood draws at baseline and each clinic study visit through the End of Treatment visit and will include systolic and diastolic blood pressure (mm Hg), pulse (beats per minute or bpm), and body temperature ( $^{\circ}$ C) after the subject has been sitting for 5 minutes. Body weight will also be recorded.

If any of the subject's measurements are outside of the normal range at screening (prior to receiving the first dose) the investigator will determine, based on medical history, whether the subject can safely continue in the study. A measurement outside the normal range may be repeated during the course of the visit for confirmation.

#### **6.2.5 Electrocardiograms**

A 12-lead ECG will be done at baseline, Week 52, and at the End of Treatment visit. Baseline and Week 52 ECGs (and early termination visits occurring in the first year) will be done at the study center on the same model unit. The end of treatment ECG may be done locally. Recorded data will include general findings, ventricular rate (bpm) and P-R, QRS, and QTc intervals (seconds). Any ECG abnormalities, as determined by the investigator, at screening will be recorded as medical history. Any clinically significant adverse change from the status at the screening visit and noted to be clinically significant by the investigator should be captured as an

AE. All ECGs conducted during the first year of the study will be assessed by a central reader and this assessment will be used as the primary data readout for the study. However, investigators are also responsible for providing their own interpretation of the ECG, and this will be captured on the ECG print out. Two copies of the ECG tracings should be retained in the subject source record. The local, end of treatment ECG will not be sent to the central reader, unless necessary in order to confirm an ambiguous result or serious abnormality.

#### **6.2.6 Physical Examinations**

Full physical examinations will be performed at baseline, Week 52, and at the End of Treatment visit and will consist of general assessments of the head, eyes, ears, nose, throat, lymph nodes, skin, extremities, and respiratory, gastrointestinal, musculoskeletal, cardiovascular, nervous, and dermatologic systems. The physical examination should be performed by the same person each time, whenever possible. Brief physical exams will be conducted every 6 months during the long-term extension portion of the study.

Physical examination abnormalities determined by the investigator to be clinically significant at screening should be recorded as medical history if they developed since the RELAY or REPLACE study.

Any clinically significant adverse change from the status at the baseline visit and noted to be clinically significant by the investigator should be captured as an AE.

#### **6.2.7 Dual-energy X-ray Absorptiometry**

DXA scans will be performed at baseline, Week 52, yearly during the long-term extension portion of the study, and at the End of Treatment visit, if it is greater than 3 months since the previous DXA scan. These scans will evaluate BMD of the lumbar vertebra (L1-L4), hip (total, trochanter, intertrochanter, Ward's triangle, and femoral neck), and  $\frac{1}{3}$  distal radius (arm). Calcium supplements should be withheld for 24 hours prior to the scan, if possible. If a subject cannot withhold the calcium supplements due to safety concern, the DXA should be performed 2 hours after the last calcium tablet has been ingested. Please note: DXA will NOT be completed at baseline if subject had a scan performed within the past 6 months within one of the previous studies.

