#### **6.4.3 Weeks 4, 8, 16, 24, 32, 40, and 48 (Visits 2 through 8) Study Clinic Visits**

The following procedures will be performed as indicated:

- Record any change in concomitant medications on the appropriate concomitant medication eCRF, including dose and frequency (all visits)
- Adverse event evaluation/update, including any incidences of hypocalcemia or hypercalcemia (all visits)
- Review the subject's diary for compliance with protocol procedures and dosing/supplement regimens (all visits)

- Collect used and unused drug cartridges and supplements (calcium and calcitriol) for assessment of accountability (all visits).
- Vital signs measurements (prior to blood draws) and weight (all visits)
- Serum 25(OH) vitamin D (all visits)
- Serum 1,25-dihydroxyvitamin D (Week 24)
- Serum calcium, phosphate, and albumin (all visits)
- Serum bone turnover markers (Weeks 8, 16, 24, and 40)
- Serum  $\beta$ -HCG pregnancy test (WOCBP only) (Weeks 16, 24, 32, 40, and 48)
- Urine pregnancy test (WOCBP only) (Weeks 4 and 8)
- Creatinine clearance (Weeks 16 and 32)
- 24-hour urine calcium, phosphate, sodium, and creatinine (Weeks 16 and 32)
- Blood sample for PTH and ECP antibodies (predose on Weeks 24 and 40)
- Blood samples for pharmacokinetic analysis will be drawn predose (0 hour) and postdose between 1 and 2 hours and between 6 and 10 hours following study drug administration (Week 48 only)
- Administration of study medication following the predose PTH blood samples for PK analysis (Week 48)
- If calcium-sparing diuretics are instituted (allowed at Week 16) and/or the dose subsequently changed, monitoring for serum potassium, sodium, and calcium will be done 1 week and again 1 month later and then at each subsequent scheduled clinic visit.
- Subjects will be provided with the following study supplies:
  - Study medication cartridges in sufficient number to supply daily doses until the next scheduled clinic visit
  - Ancillary injection supplies (ie, alcohol swabs, needles, etc.)
  - Calcium (carbonate or citrate) and calcitriol supplements in sufficient quantity to supply daily doses until the next scheduled clinic visit
  - Collection container for 24-hour urine (Dispense on Weeks 8, 24, and 48 for collections prior to Weeks 16, 32, and 52)

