#### **6.4.6 End of Treatment Visit or Early Termination**

- Record any change in concomitant medications on the appropriate concomitant medication eCRF, including dose and frequency.
- Adverse event evaluation/update, including any incidences of hypocalcemia or hypercalcemia
- Full physical examination
- Vital signs measurements (prior to blood draws) and weight
- 12-lead ECG (may be local)
- A BMD test by DXA (if previous DXA was  $\geq 3$  months prior)
- Blood samples for serum chemistries (including calcium and phosphate), hematology, serum 25(OH) vitamin D, serum 1,25-dihydroxyvitamin D, creatinine clearance, and bone turnover markers
- Blood sample for PTH and ECP antibodies (See Section 6.2 for additional follow-up for subjects who develop antibodies specific to PTH.)
- Administration of the last dose of study medication following the predose PTH samples
- Urinalysis
- 24-hour urine calcium, phosphate, sodium, and creatinine
- Serum  $\beta$ -HCG pregnancy test (WOCBP only)

- Review the subject's diary
- Collect used and unused drug cartridges and pen injectors, for assessment of accountability, and subject diaries.
- Subjects will either be prescribed appropriate oral calcium and/or active vitamin D to compensate for the cessation of NPSP558 (rhPTH[1-84]) or may opt to continue treatment on commercial drug (Natpara). Subjects who continue treatment with Natpara will continue to be monitored under the care of a physician according to approved labeling instructions.

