5.4. Handling of Dropouts or Missing Data

5.4.1. Handling of Dropouts or Missing Data for Efficacy Analysis

The daily dose of calcium and vitamin D metabolite/analog will be computed based on both investigator prescribed data and subject diary data. The investigator prescribed data will be considered as the primary method for all efficacy analysis endpoints.

The daily dose of calcium and vitamin D metabolite/analog based on investigator prescription will be determined by using the latest prescribed dose prior to the assessment date of albumin corrected calcium for each analysis visit. To avoid the effect of potential fluctuation of the supplemental medication dose, the prescribed supplemental medication dose at Visit 1 (BL visit) will be excluded from the derivation of the baseline dose and the prescribed dose at the Visit 9 (week 52) for subjects who complete the treatment or Early Termination Visit. Subjects that discontinued early will be excluded from the derivation of the post-baseline prescribed dose.

The average daily dose of calcium and vitamin D metabolite/analog based on subject diaries will be calculated as the average daily dose of a 14-day interval. The 14-day interval for each current analysis visit includes the dose reported during the 14 days on or prior to the assessment date of albumin corrected calcium. However, this 14-day interval should not include or go beyond the assessment date of albumin corrected calcium for the previous analysis visit. If the number of days from the previous albumin corrected calcium date to the current assessment date is less than 14 days, the actual number of days during the two analysis visits will be used to calculate the average daily dose. If the number of days from the previous albumin corrected calcium date to the current assessment date is less than 9 days, the average daily dose will not be calculated and will be classified as missing. Diary data after the last dose date of study drug will be excluded from the derivation.

A missing daily dose of calcium and vitamin D from subject diaries will not be imputed. A minimum 9 days of non-missing data from the intervals is required, otherwise the average daily dose will be classified as missing. Because recordings of dose of calcium and vitamin D metabolite/analog may be missing on different days, different days within the interval may be used in the computation for the daily dose of calcium and for the daily dose of vitamin D metabolite/analog.

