6.7.2. Other Analyses

Mean percentage changes from baseline in supplemental oral calcium and supplemental calcitriol dosage at each visit

The absolute and percentage changes from baseline will be summarized at each visit. No formal statistical test will be done.

Proportion of subjects achieving the primary endpoint at each visit

The number and percentage of subjects achieving the primary efficacy endpoint will be presented by visit. No formal statistical test will be done.

Mean percentage change from baseline in 24-hour urine calcium excretion

The absolute and percentage changes from baseline will be summarized by visit. No formal statistical test will be done.

Impact of calcium source (carbonate vs. citrate) on response

The number and percentage of subjects meeting the criteria of being responders will be presented by visit and by calcium source (carbonate vs. citrate). No formal statistical test will be done.

Impact of calcium-sparing diuretics on serum and urinary calcium

The number and percentage of subjects who use at least one calcium-sparing diuretics during the study will be presented.

The urinary calcium will be listed for subjects who received calcium-sparing diuretics during the study. No formal statistical test will be done.

Proportion of subjects that maintain a calcium phosphate product in the range of 35 to 55 mg²/dL²

Calcium phosphate product will be classified as normal (35 - 55 mg²/dL²), or abnormal (including low and high). The number and percentage of subjects with maintenance of a calcium phosphate product in the normal range will be presented by visit. No formal statistical test will be done.

Distribution of subjects by rhPTH[1-84] doses at the End of Treatment Visit

The number and percentage of subjects at different dose levels at the EOT visit will be summarized. No formal statistical test will be done.

Change from baseline in bone turnover markers (bone-specific alkaline phosphatase, serum carboxy-terminal telopeptide of type I collagen, serum procollagen type I amino-terminal propeptide, and osteocalcin), PTH and ECP antibodies, and BMD by DXA

The absolute and percentage changes from baseline will be summarized by visit. No formal statistical test will be done. For DEXA, Z-scores will also be presented and summarized.

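### The 24-hour calcium hold before DXA may overlap the 24-hour urine collection at Week 52 and the annual visits, so 6 of the 18 scheduled urine calcium results to Month 72 may not be comparable with the rest

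*Protocol*

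**What the plan says.** Protocol Section 6.2.7 sets the scan schedule: "DXA scans will be performed at baseline, Week 52, yearly during the long-term extension portion of the study", and again at End of Treatment. Section 6.4.6 makes that last scan conditional ("A BMD test by DXA (if previous DXA was" at least 3 months earlier). The RACE baseline scan is often omitted: "DXA will NOT be completed at baseline if subject had a scan performed within the past 6 months".

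Before a scan, "Calcium supplements should be withheld for 24 hours prior to the scan, if possible". For a subject who cannot stop for safety reasons, "the DXA should be performed 2 hours after the last calcium tablet has been ingested". The DXA footnotes to Protocol Tables 6-1 to 6-3, repeated in SAP Tables 4.1 to 4.3, give the same hold and exception but drop the qualifier at the end of the first sentence. The two wordings should be reconciled.

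The 24-hour urine is due at baseline, Weeks 16, 32 and 52, every 4 months in the extension, and End of Treatment (Section 6.2.3). It is collected before the visit; the container instruction in Section 6.4.3 reads "Dispense on Weeks 8, 24, and 48 for collections prior to Weeks 16, 32, and 52". Section 6.4.4 lists both the urine and the DXA for Week 52.

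For 24-hour urine calcium, SAP Section 6.7.2 says: "The absolute and percentage changes from baseline will be summarized by visit". SAP Section 6.8.2 counts subjects with post-baseline values above 300 mg (men) or 250 mg (women) as markedly abnormal. For the diary-based supplement dose, the SAP Section 5.4.1 interval "includes the dose reported during the 14 days on or prior to the assessment date of albumin corrected calcium".

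**The concern.** Urine calcium is an efficacy variable, and incidence of hypercalciuria is a safety endpoint. Protocol Section 1.1 itself names oral calcium supplementation as a contributor to hypercalciuria. A site that carries out Week 52 or an annual visit as listed, with a morning scan and a urine collection made the day before, collects that urine while supplements are stopped. At the urine visits without a scan, the same subject collects on usual supplements.

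A dip at Week 52 and at each annual visit could then come from the measurement conditions and still be read as a change over time on treatment. Section 3.1 also uses urine calcium when diuretics are adjusted. Nothing planned would show which results were obtained under a hold. Because the hold has exceptions, the mix may also differ between subjects at the same visit.

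**Working it through.** The plan has no figure of its own to reproduce: no sample size was calculated and no tests are planned. The check is a schedule count plus a bound on the diary dose.

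**1. Which urine collections share a visit with a scan** (Protocol Section 6.2.3, Tables 6-1 to 6-3)

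| Visits to Month 72 | Urine | DXA | Count |
|---|---|---|---|
| Weeks 16, 32 | yes | no | 2 |
| Week 52 | yes | yes | 1 |
| Months 16, 20, 28, 32, 40, 44, 52, 56, 64, 68 | yes | no | 10 |
| Months 24, 36, 48, 60, 72 | yes | yes | 5 |

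The extension has (72 − 16)/4 + 1 = 15 collections, and 3 + 15 = 18 in all. With a scan: 1 + 5 = 6. Without: 2 + 10 = 12. End of Treatment comes on top of this, and only when a scan is due.

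After Month 72 the urine is also due at Months 76 and 80, making 20 collections. Table 6-3 puts Month 80 in a column that includes DXA, while its note restarts the visit cycle at Month 74. The count is therefore 6 or 7 of 20, depending on which is followed.

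**2. How far the two periods can overlap**

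Let h be the hours from the end of the urine collection to a later scan. The overlap with a 24-hour hold is max(0, 24 − h) hours.
- Collection ends as the scan takes place (h = 0): 24 hours, complete overlap.
- Scan a day or more after the collection ends (h ≥ 24): none.

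The documents do not fix h. They say that the urine precedes the visit but not by how long, and they do not require the scan on the day of the visit. Windows are ±7 days in year 1, ±2 weeks in the extension and ±1 week at End of Treatment. Any overlap from 0 to 24 hours fits the plan.

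**3. Supplement dose**

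- Primary method (SAP Sections 5.4.1 and 6.7): the latest prescribed dose before the calcium assessment. A one-day hold changes it by 0.
- Supportive method: the diary average over up to 14 days, with at least 9 non-missing. One day without calcium among D days multiplies the average by (D − 1)/D.

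| | D = 14 | D = 9 |
|---|---|---|
| Fall in average, 1/D | 7.1% | 11.1% |
| Usual reduction that would read as 50%: 1 − 0.5 × D/(D − 1) | 46.2% | 43.8% |
| Usual dose that would read as 500 mg: 500 × D/(D − 1) | 538 mg | 562.5 mg |

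These are upper limits. They assume that the whole day's calcium was stopped and that the held day is in the interval. Calcitriol is not part of the hold.

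**4. Serum calcium**

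Protocol Section 5.3.2 places the blood draw before the injection, and the morning calcium after it, at every visit. A hold can therefore change only the previous day's doses. Scheduled albumin in the extension comes only with the yearly and End of Treatment chemistry panels (Section 6.2.3), so scheduled albumin-corrected values do fall at visits where a scan may be due.

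**The case against.** The strongest reply is that nothing forces an overlap. The hold has exceptions, same-day scanning is not required, and the visit windows already let a site separate the two. This stands, and it is why the point says may overlap. It does not remove the point: the footnotes make holding the default, the visit lists group the procedures together, and the analysis cannot tell which results were affected.

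A second reply is that the subject-level hypercalciuria count is partly protected, because any of the 12 collections without a scan can still qualify a subject. That is right. The by-visit urine summaries are the more exposed output, although a dip confined to scan visits would at least be visible there.

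A reader might infer more than the documents support, in four ways:

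- **The responder endpoint is measured with calcium withheld.** The dose conditions use the prescribed dose in the primary analysis. Any serum effect is limited to the previous day's doses and has no clear direction: lower calcium makes normalized or maintained harder to meet and the upper limit easier. The End of Treatment scan is conditional, and the SAP's EOT value (Section 5.1) is the last available measurement, which need not come from a scan visit.
- **The fall in urine calcium is wrongly credited to rhPTH[1-84].** For subjects who completed REPLACE or RELAY, SAP Section 5.3.2 takes the baseline from those studies. Whether a hold applied there is not stated. If it did, the scan visits would be the matched comparison.
- **The effect is 75 to 100 mg/day per 500 mg withheld.** This follows from the absorption figures in Protocol Section 1.1 (500 × 0.30 to 0.40 × 0.5). But those figures describe dietary calcium in general, up to half is an upper limit on what returns to the gut, the same section reports malabsorption in hypoparathyroidism, and nothing says how much of a change appears within one day.
- **Affected samples should leave the main analysis.** With about 50 subjects, no formal testing and an effect of unknown size, that would lose Week 52 and annual data for an uncertain gain.

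**Conclusion.** The point holds for urine calcium and hypercalciuria. At 6 of the 18 scheduled post-baseline collections to Month 72, and at End of Treatment when a scan is due, the urine may be collected during a calcium-supplement hold that does not apply at the other 12. Comparisons between visits within RACE may therefore mix two measurement conditions, and the plan neither prevents nor identifies this.

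The size cannot be computed from the documents. It depends on how much calcium a subject still takes at that visit and on how many sites scan directly after the collection. Subjects taking no oral calcium are unaffected. The bias in change from baseline has no known direction. The effect on supplement dose is zero for the primary analysis and at most 7.1% to 11.1% for the supportive diary average. Serum calcium is a secondary matter. Whether, or for how long, calcium should be withheld is a clinical question and is not judged here.

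**What to change.** Leave the hold itself as it is.

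- **Protocol Section 6.2.7 and the DXA footnotes to Tables 6-1 to 6-3:** state that the 24-hour urine collection is to be finished before the hold starts, or that the scan is done on another day within the visit window. Record for each scan whether calcium was withheld.
- **SAP Sections 6.7.2 and 6.8.2:** use DXA, urine-collection and diary dates to flag collections that overlap a hold. Keep the all-data summaries of urine calcium and hypercalciuria, and add a version without the flagged samples.
- **SAP Section 5.4.1:** leave hold days out of the supportive diary average, and say whether the 9-day minimum is counted before or after that exclusion. If after, an interval with exactly 9 days drops to 8 and becomes missing.

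The cost is slightly more scheduling, a separate scan appointment for some subjects, and one extra summary. DXA and central laboratory results are already transferred to the sponsor (Protocol Section 7.1), and diaries already record supplement regimens (Section 5.3.3). The SAP part can therefore be done from existing data even if the protocol text can no longer be changed in time.
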